7.2 Efficacy Outcomes

Overall pain assessment at rest using NPRS will be performed every 2 hours ((± 15 minutes) post-dose after the subject is awake and lucid from surgery, until discharge. Assessments will also be made after subjects are discharged on Days 6-29 and will be entered into the Pain Assessment Diary (see Section 7.1.1.31.1 of the protocol).

Pain assessment after an activity using NPRS-A will be performed at baseline (prior to surgery), every 8 hours (± 15 minutes) post-dose on Day 1, and every 6 hours on day 2 and after, after the subject is awake and lucid from surgery until discharge. The Investigator will ask subjects to sit up in the bed unassisted at an angle of approximately 45 degrees or more, swing legs out, put feet down, stand up, and walk approximately 10 feet. Subjects will then be asked to rate their level of worst pain when performing the activities using the NPRS-A. NPRS-A will also be assessed at each follow-up visit on days 8, 15, and 29 (End of Study (EOS)/ Early Termination (ET)).

During the in-patient period (up to Day 5), NPRS / NPRS-A assessments scheduled between 00:00 and 06:00 may be skipped if the subject is sleeping. However, the 12-hour pain assessment must be completed even when the assessment falls between 00:00 and 06:00.

NPRS and NPS-A are ranged based on an 11-point numerical scale, where 0 means no pain and 10 means the worst pain imaginable.

In the event rescue medication is used, an assessment of pain using the NPRS prior to administering rescue medication will be recorded. If subjects cannot perform NPRS-A prior to taking rescue medication due to intolerable pain, this assessment may be omitted.

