### Efficacy Assessments

- Overall pain scores at rest using the NPRS
  - NPRS is self-assessed by the study subject for their current pain according to an 11- point numeric pain rating scale (NPRS; 0 - 10) where 0 equates to no pain, and 10 equates to the worst pain imaginable.
  - Pain assessment starts once the subject is awake and lucid from surgery at every 2 hour timepoint ( $\pm 15$  minutes) until 96 hours (time of discharge). Time 0 is the time of intraoperative drug administration.
  - NPRS assessments scheduled between 00:00 and 06:00 may be skipped if the subject is sleeping except for the 12 hour pain assessment if it falls between 00:00 and 06:00.
  - On the mornings (10:00  $\pm 4$  hours) of Days 6-29 (inclusive), subjects will be encouraged to record their worst pain at rest since the last assessment of their pain intensity in their take home Pain Assessment Diary.
- Pain assessment using NPRS-A
  - After completing the overall pain assessment at rest, the investigator will ask the subjects to sit up in the bed unassisted at an angle of approximately 45 degrees or more, swing legs out, put feet down, stand up, and walk for approximately 10 feet. Subjects will then be asked to rate their level of worst pain when performing the activities using the NPRS-A. Pain assessments for NPRS-A will be conducted every 8 hours on Day 1, and every 6 hours on Day 2 and after.
  - NPRS-A assessments scheduled between 00:00 and 06:00 may be skipped if the subject is sleeping except for the 12-hour pain assessment if it falls between 00:00 and 06:00.
  - At visits on Days 8, 15, and 29, the NPRS-A assessment will be performed.
- PGA of pain control
  - Each subject will be asked the following question: Overall, please rate how well your pain has been controlled during the last 24 hours? Poor (0), Fair (1), Good (2), or Excellent (3).
- Use of rescue medications over the post-surgical assessment periods

- In the event rescue medication is used, pain assessments using NPRS and NPRS-A will be recorded immediately prior to administering rescue medication.

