#### **7.1.1.26 Pain Assessment after Walking (NPRS-A)**

At baseline prior to surgery, and then every 8 hours ( $\pm 15$  minutes) post-dose on Day 1, and every 6 hours on day 2 and after, after the subject is awake and lucid from surgery until discharge, the Investigator will ask subjects to sit up in the bed unassisted at an angle of approximately 45 degrees or more, swing legs out, put feet down, stand up, and walk approximately 10 feet. Subjects will then be asked to rate their level of worst pain when performing the activities using the NPRS-A, on an 11-point numerical scale, where 0 means no pain and 10 means the worst pain imaginable ([Appendix 5](#)) while they were walking.

NPRS-A assessments scheduled between 00:00 and 06:00 may be skipped if the subject is sleeping. However, the 12-hour pain assessment must be completed even when the assessment falls between 00:00 and 06:00. Assessments will also be made at each follow up visit on Days 8, 15, and 29.

In the event rescue medication is used, an assessment of pain using the NPRS prior to administering rescue medication will be recorded. If subjects can not perform NPRS-A prior to taking rescue medication due to intolerable pain, this assessment may be omitted.

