#### **7.1.1.31.2 Rescue Medication Diary**

Subjects will be encouraged to record all rescue medication usage in their take-home Rescue Medication Diary. See [Section 7.2](#) for details regarding allowable rescue medication. Subjects will be instructed to complete an entry in their Pain Assessment Diary prior to taking rescue medication. Completion of the Rescue Medication Diary will start immediately following discharge on Day 5. In the event rescue medication is taken by the subject following discharge on Day 5, subjects will be encouraged to record their pain scores prior to taking the rescue medication ([Appendix 8](#)). In the event subjects can not perform NPRS-A due to intolerable pain, this assessment may be omitted.

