### 10.2 Statistical Hypotheses

The primary efficacy objective is to estimate the reduction of pain with EB-001, assessed as the difference in AUC for the NPRS pain scores over the 12-96 hours postsurgical period.

The null hypothesis is that the AUC for the EB-001 arm is greater than or equal to that of the placebo arm. The alternative hypothesis is that the AUC for EB-001 is smaller (indicating less pain) than that for placebo.

$$H_0: AUC_{EB-001} \geq AUC_{Placebo}$$

$$H_A: AUC_{EB-001} < AUC_{Placebo}$$

While not a formally powered study, a one sided hypothesis that the AUC for NPRS and NPRS-A will be used to inform the primary clinical hypothesis and support this objective.

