7. EFFICACY EVALUATION

7.1 Overview of Efficacy Analysis Issues

7.1.1 *Handling of Dropouts or Missing Data*

If a subject receives protocol specified rescue medication, a windowed LOCF imputation method will be used and the pre-rescue pain NPRS/NPRS-A score for each assessment (pain at rest, pain after walking) will be carried forward for 4 hours. Intermittent missing pain scores (due to subject sleeping, etc.) will not be imputed, and AUC will be calculated based on non-missing values.

In AUC analyses, no other imputation will be performed for subjects who have missing values due to early drop out. In addition, there will be no imputation of missing data for safety or other efficacy assessments.

7.1.2 *Assessment Time Windows*

Assessment times will be based on the nominal protocol-specified assessment times.

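### An NPRS-A score omitted before rescue because pain is intolerable has no substitute in the SAP, so the descriptive NPRS-A AUC is biased low whenever the omitted score exceeds its neighbours

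*SAP*

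**What the plan says.** **Omission.** SAP 7.2 allows it: "If subjects cannot perform NPRS-A prior to taking rescue medication due to intolerable pain, this assessment may be omitted". Protocol 7.1.1.26 has the same permission for the in-patient stay, and Protocol 7.1.1.31.2 extends it to the diary after discharge: "In the event subjects can not perform NPRS-A due to intolerable pain, this assessment may be omitted". For resting NPRS, the same sections require a score before rescue and allow no exception on grounds of pain.

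**Rescue rule.** SAP 7.1.1 states that "a windowed LOCF imputation method will be used and the pre-rescue pain NPRS/NPRS-A score for each assessment" is carried forward for 4 hours. SAP 7.3.1 applies this to the AUC: the score taken before rescue stands for the next 4 hours and what was observed in that period is ignored.

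**Other gaps.** SAP 7.1.1: "Intermittent missing pain scores (due to subject sleeping, etc.) will not be imputed, and AUC will be calculated based on non-missing values". Apart from the rescue rule, nothing else is imputed.

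**Conflict within the protocol.** The Efficacy Assessments part of the Protocol Summary has no exception: "pain assessments using NPRS and NPRS-A will be recorded immediately prior to administering rescue medication".

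**Status of NPRS-A.** It is a secondary endpoint (SAP 7.2.2), and SAP 7.3.1 computes its AUC with the same trapezoidal formula as for NPRS. The study stopped after 23 subjects were randomized, and SAP sections 1 and 3 limit the analysis to descriptive summaries without testing.

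**The concern.** The 4-hour carry-forward is there so that relief from rescue medication is not counted as low pain. It can work only if a pre-rescue score was recorded. The permission to omit removes that score in the episodes where activity pain is at its worst, and no section names a substitute. The general rule for intermittent gaps, whose own example is a sleeping subject, then applies to scores that are missing because pain was intolerable. That missingness is informative.

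What happens next depends on timing and on how the programmer reads the SAP:

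- The gap is bridged by the trapezoid between the neighbouring scores.
- An older NPRS-A is carried forward, if windowed LOCF is taken to mean the last score available.
- A scheduled NPRS-A taken within 4 hours after rescue stays in the AUC, because no pre-rescue value exists to override it.

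All three give a lower AUC than the plan would have given with the score recorded, provided that the omitted score was above its neighbours. At stake is the level of activity pain reported for each group and, if omission is uneven, the comparison between groups.

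**Working it through.** **The plan's own figure.** The documents give no figure for NPRS-A or for omissions. The only related figure that can be checked is the power in Protocol 10.5. With 22 per arm, one-sided alpha 0.05, difference 110 and SD 170, the noncentrality is 110 / (170 × √(2/22)) = 2.146. The t-test on 42 degrees of freedom then has power 0.680, which agrees with the stated figure of about 67%. It concerns resting NPRS in Stage 2 and plays no part below.

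**Inputs from the documents.** NPRS-A every 8 hours on Day 1 and every 6 hours from Day 2 (SAP 7.2); the 4-hour hold and the trapezoidal rule (SAP 7.1.1, 7.3.1).

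**Assumed inputs.** Window 24 to 36 h with scheduled scores at 24, 30 and 36 h. The score is 6 at 24 h and 6 at 36 h, and 4 at 30 h when that score is observed after rescue. The pre-rescue score P is 8, 9 or 10.

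**Recorded, rescue at 28 h.** P is held from 28 to 32 h and overrides the 30 h score. AUC = (6+P)/2 × 4 + 4P + (P+6)/2 × 4 = 24 + 8P, which is 88, 96 or 104.

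**Omitted, by route:**

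| Route | AUC if omitted | Loss for P = 8, 9, 10 |
|---|---|---|
| Rescue at 28 h; the relieved 4 at 30 h is used | (6+4)/2 × 6 + (4+6)/2 × 6 = 60 | 28, 36, 44 |
| Rescue at 30 h; the scheduled 30 h score is the one omitted and is bridged | 6 × 12 = 72 | 16, 24, 32 |
| Rescue at 28 h; the older score of 6 is held for 4 h | 6 × 12 = 72 | 16, 24, 32 |

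In the second row the recorded AUC is (6+P)/2 × 6 + 4P + (P+6)/2 × 2, again 24 + 8P.

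**Rescue whose hold ends before the next scheduled score.** With rescue at 25 h the hold ends at 29 h, so the 30 h score of 4 stays in either way. Recorded: (6+P)/2 × 1 + 4P + (P+4)/2 × 1 + (4+6)/2 × 6 = 35 + 5P, which is 75, 80 or 85. Omitted: 60. The loss is 15, 20 or 25.

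**No loss.** If every score, including the omitted one, is 8, both versions give 8 × 12 = 96.

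**Between arms.** The placebo-minus-active difference shrinks by L × (k_placebo − k_active), where L is the mean loss per omission and k the mean number of omissions per subject. Take L as 8 to 20, set below most of the figures above because some episodes lose little or nothing. Two omissions per placebo subject against one per active subject shrink the difference by 8 to 20. Equal rates and equal losses leave it unchanged. L and both k are assumptions.

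**The case against.** The strongest reply is that little depends on this. NPRS-A is secondary, 23 subjects were randomized and nothing will be tested. Individual NPRS-A scores are plotted and listed, and rescue is listed by time of dosing, so a careful reader could find a rescue without a paired NPRS-A. The SAP does not name this case, and windowed LOCF could mean carrying an older NPRS-A forward. All of this stands, and it limits the consequence. It does not remove the gap: the older-score reading still loses 16 to 32 score-hours in the illustration, and the AUC itself would carry no flag.

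Some stronger readings are tempting but not supported:

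- **The primary endpoint is biased.** Resting NPRS must be recorded before rescue, so its carry-forward is not broken by this permission.
- **NPRS-A belongs to the primary hypothesis.** Protocol 10.2 says that "a one sided hypothesis that the AUC for NPRS and NPRS-A will be used to inform the primary clinical hypothesis", but the sentence is incomplete, the objective above it is defined on NPRS over 12 to 96 hours, and the SAP tests neither measure.
- **Relieved scores always replace the worst pain.** This is literal only if a scheduled NPRS-A falls within 4 hours after rescue. With assessments 6 or 8 hours apart, some episodes have none.
- **A large share of the effect is lost.** A reader might take (9 − 5) × 6 = 24 score-hours per episode, assume two more episodes per placebo subject, and set 48 against the protocol's difference of 110. No section supports that frequency, and 110 is a resting-NPRS assumption for a Stage 2 that did not take place.

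**Conclusion.** The point holds for the level of the NPRS-A AUC. Following the plan as written biases it low whenever the omitted score exceeds its neighbours. The loss is roughly 16 to 44 score-hours per episode where a scheduled score falls inside the hold or is itself the omitted one, 15 to 25 in the example where neither applies, and nothing where the neighbours are equal to the omitted score. These sizes rest on assumed scores.

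A distorted treatment difference is only a possibility. It requires omissions, or the loss per omission, to differ by arm; more omissions on placebo would then understate any benefit of EB-001. How far cannot be computed, because the documents give neither an omission frequency nor a distribution of NPRS-A. The consequence is modest, but the rule applies one-sided handling to informative missingness and can be repaired cheaply.

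**What to change.** Before database lock, add the following to SAP 7.1.1 and 7.3.1:

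1. Identify every in-patient rescue that has a pre-rescue NPRS but no pre-rescue NPRS-A. Use the recorded reason for omission where there is one, and count these episodes by treatment group.
2. For the 4 hours after each such rescue, do not use the observed NPRS-A. Compute the NPRS-A AUC twice: with the concurrent pre-rescue resting NPRS carried forward as a lower bound, and with 10 as an upper bound.
3. Report both beside the as-planned result, and state that the lower bound assumes activity pain to be at least as high as resting pain.
4. Reconcile the Efficacy Assessments text in the Protocol Summary, which has both scores recorded before rescue without exception, with Protocol 7.1.1.26 and SAP 7.2, which allow the omission.

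The cost is some SAP wording, one count and two extra runs of the NPRS-A AUC. The imputed values are bounds and not observations. Because the study has ended, the reason for an omission may not be recoverable for every episode, so the count may include scores missing for other reasons; it should be shown by recorded reason, with unknown as a category.

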7.2.1 Primary Efficacy Endpoint

Area under the curve (AUC) of subject's assessment of pain using NPRS between 12- and 96-hour post-surgery (AUC₁₂₋₉₆).

7.2.2 Secondary Efficacy Endpoints

- AUC assessment of overall pain profile using NPRS:
 - Over the first 96 hours post-surgery (AUC₀₋₉₆)
 - Over the first 72 hours post-surgery (AUC₀₋₇₂)
 - Over the first 48 hours post-surgery (AUC₀₋₄₈)
 - Over the first 24 hours post-surgery (AUC₀₋₂₄)
 - Over the period of 12 to 24 hours post-surgery (AUC₁₂₋₂₄)
 - Over the period of time t to 96 hours post-surgery ((AUC_{t-96}), whereas t is any time during confinement
- Pain assessment at rest after discharge using NPRS at Days 6 through 29.
- Pain assessment after sitting up in the bed unassisted at an angle of approximately 45 degrees or more, swinging legs out, putting feet down, standing up, and walking approximately 10 feet using NPRS-A (NPRS administered after an activity) over the first 96 hours and at Days 8, 15, 29.
- Patient global assessment (PGA) of pain control
- Use of rescue medications over various postsurgical periods

7.3 Analysis Methods

7.3.1 AUC Outcomes

All AUC calculations will be done using the standard trapezoidal rule

$$AUC = \sum_{i=0}^x \left(\frac{NPRS_i + NPRS_{i+1}}{2} \right) * (T_{i+1} - T_i)$$

Where: $NPRS_i$ = NPRS at time i , and $(T_{i+1} - T_i)$ is the Time difference in hours between time i and time $i+1$. The AUC calculation of NPRS-A will be calculated using the same formula, substituting $NPRS_{-A_i}$ in place of $NPRS_i$.

In the event that protocol specified rescue medication is used during the time period of AUC calculation, for purposes of AUC calculation, the NPRS and/or NPRS-A score taken prior to the dispensation of rescue medication will be used as the NPRS and/or NPRS-A score for the following 4-hour period and the observed AUC score will be ignored.

The individual NPRS and NPRS-A scores through Day 5 (prior to discharge) will be presented graphically over time by cohort and presented in subject listings.

The computed AUCs will be listed for the individual subjects along with the respective endpoints that they were calculated on.

7.3.2 *NPRS and NPRS-A Outcomes*

The individual NPRS and NPRS-A outcomes after discharge will be summarized at each time point similar to the primary analysis.

7.3.3 *Patient Global Assessment (PGA) of Pain Control*

To assess pain control, each subject will be asked the following question: "Overall, how well your pain has been controlled during the last 24 hours?" at 96 ± 2 hours (Days 5), and on Days 8, 15, and 29 (EOS/ET), using a 4-point categorical scale (Poor (0), Fair (1), Good (2), Excellent (3)).

PGA summary tables will include the proportion of subjects with each score, by cohort and time point. PGA scores will be listed.

7.3.4 *Rescue Medication*

Rescue medication when needed is a maximum of 5 doses of 50 µg IV Fentanyl (up to 250 µg total) during the first 120 minutes after post-anesthesia care unit (PACU) arrival. After the first 120 minutes have elapsed, subjects during confinement may only receive oxycodone 5 mg every 4 hours, PRN. Following discharge from the hospital, subjects may use 500 mg acetaminophen PRN, a maximum of 6 times per day (not to exceed 3 g total dose in 24 hours). Subjects will be instructed not to take rescue medication until their pain reaches at least a moderate intensity, and to complete an entry in their Pain Assessment Diary prior to taking rescue medication. All post-discharge rescue medication usage must be recorded in the Rescue Medication Diary. Subjects' rescue use will be captured on the Rescue Medication eCRF during the Inpatient portion of the study and in the Subject Rescue diary after discharge until Day 29. If additional rescue medication, other than the study rescue medications, appear on the concomitant medications page and can be identified, those medications will also be included in summaries as described below.

The summary will include all rescue taken by subjects regardless of their status (discontinued from efficacy or not).

Total amount of opioids (MEQ) used during the first 96 hours will be summarized overall (0-96hrs). [Table 7-1](#) will be used to calculate the morphine milligram equivalents (MEQ) for each medication. The total opioid consumption for each day for each subject will be calculated as the sum of the MEQs of all of the medications taken on that day. For example, if a subject takes 5 MEQ morphine on Day 1 and Day 2, and 10 MEQ of Oxycodone on Day 2, the total consumption for Day 1 is 5 MEQ, and the total consumption for Day 2 is 15 MEQ. Subjects that take no opioids on a day will have a total opioid consumption value of zero for that day.

Table 7-1 Table of Morphine Milligram Equivalents
(from cdc.gov/drugoverdose/pdf)

[figure not shown]
Opioid (Doses in mg/day)	Conversion Factor
Codeine	0.15
Fentanyl transdermal (in mcg/hr)	2.4
Hydrocodone	1
Hydromorphone	4
Morphine	1
Oxycodone	1.5
Oxymorphone	3

Total dose of Oxycodone used during the first 96 hours and the number of doses of Oxycodone will both be summarized separately. Summaries will be shown both for overall (0-96hrs). Total Oxycodone use will also be presented graphically overall and by cohort.

A by-subject listing presenting the use of rescue medication by time of dosing will be given.

[figure not shown]
Sponsor: Bonti, Inc.
Protocol Number: EB001-ABD201

Statistical Analysis Plan Version 1.0
Effective Date: 07NOV2018

[figure not shown]
Sponsor: Bonti, Inc.
Protocol Number: EB001-ABD201

Statistical Analysis Plan Version 1.0
Effective Date: 07NOV2018

Sponsor: Bonti, Inc.
Protocol Number: EB001-ABD201

Statistical Analysis Plan Version 1.0
Effective Date: 07NOV2018

[figure not shown]

Sponsor: Bonti, Inc.
Protocol Number: EB001-ABD201

Statistical Analysis Plan Version 1.0
Effective Date: 07NOV2018

Sponsor: Bonti, Inc.
Protocol Number: EB001-ABD201

Statistical Analysis Plan Version 1.0
Effective Date: 07NOV2018

Sponsor: Bonti, Inc.
Protocol Number: EB001-ABD201

Statistical Analysis Plan Version 1.0
Effective Date: 07NOV2018

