If a subject requests rescue medication, the pre-rescue pain NPRS and NPRS-A assessments will be carried forward for 4 hours. Handling of missing data for subjects who discontinue the study will be specified in the SAP.

[figure not shown]

[REDACTED]

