3. GENERAL ANALYSIS AND REPORTING CONVENTIONS

This section discusses general policies to be employed in the analysis and reporting of the data from the study. Departures from these general policies are provided in the specific detailed

sections of this SAP. When this situation occurs, the rules set forth in the specific section take precedence over the general policies.

All continuous study assessments will be summarized by treatment and time point (as applicable) using the descriptive statistics n, mean, SD, median, and range (minimum, and maximum). All of the categorical study assessments will be summarized by treatment and time point (as applicable) using frequency counts and rates of occurrence (%). Changes from baseline for continuous outcomes will be presented as their corresponding continuous measures for post-baseline visits. All study data will be listed by treatment dose level, subject, and time point (as applicable). The placebo group will consist of the placebo subjects from each of the different cohorts combined. For all analyses, the pooled set of placebo subjects from the various cohorts will be considered the placebo group.

No preliminary rounding will be performed; rounding will only occur after the analysis. To round, consider the digit to the right of the last significant digit: if <5 , then round down; if ≥ 5 , then round up. Means and medians will be presented with one more decimal place than the precision of the data. SDs will be presented with two more decimal places than the precision of the data. Percentages will be presented with one decimal place. Minimums and maximums will be presented with the same precision as the original data.

The domain (Study data tabulation Model [SDTM]) and analysis (Analysis Data Model [ADaM]) data sets will be taken as input to the [redacted] programs that generate the report-ready tables, figures and listings. The submission ready SDTM and ADaM data sets will be provided to the sponsor along with display deliveries.

For all summaries, the pooled set of placebo subjects from the various cohorts will be considered the placebo group.

No testing will be conducted due to early termination of the study.

The following conventions will be used throughout the study analysis:

- Stop Time of dose administration is considered time 0.
- Assessment visit times are defined by time of treatment administration.

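### SAP 7.1.1 and 7.3.1 word the 4-hour rescue carry-forward differently, so it is unclear whether rescue taken shortly before 12 h is corrected in AUC12-96 and AUC12-24

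*SAP*

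**What the plan says.** Three places state the rule.

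- **Protocol Summary**, after the sample size text: "If a subject requests rescue medication, the pre-rescue pain NPRS and NPRS-A assessments will be carried forward for 4 hours". No AUC window is mentioned.
- **SAP 7.1.1**, the missing-data section: "If a subject receives protocol specified rescue medication, a windowed LOCF imputation method will be used". Under this method the score recorded before rescue "will be carried forward for 4 hours". Again there is no window condition. The same section then says "In AUC analyses, no other imputation will be performed for subjects who have missing values due to early drop out", so its rescue rule is meant to cover the AUCs.
- **SAP 7.3.1** (AUC Outcomes) sets a condition: "In the event that protocol specified rescue medication is used during the time period of AUC calculation". Where it is met, the value before rescue becomes the "score for the following 4-hour period and the observed AUC score will be ignored".

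The endpoints in SAP 7.2.1 and 7.2.2 include windows that start at time 0 (AUC0-24, AUC0-48, AUC0-72, AUC0-96) and windows that start later (AUC12-96, which is primary; AUC12-24; and AUCt-96). SAP 7.2 schedules NPRS every 2 hours and makes the 12-hour score compulsory even overnight. SAP 7.3.4 makes oral rescue available as needed throughout confinement, so rescue between 8 and 12 h can occur.

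**The concern.** The carry-forward stops rescue from making a subject look less painful. A dose at 11 h is not taken inside the 12-96 h window. A programmer who follows 7.3.1 to the letter would therefore keep the observed 12 h and 14 h scores in AUC12-96 and AUC12-24, although both lie within 4 hours of the dose. A programmer who follows 7.1.1 would overwrite both.

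Two things follow from the literal reading. First, subjects rescued just before 12 h get an AUC that is too low; if placebo subjects are rescued more often in that span, the placebo-active difference shrinks. Second, nested endpoints disagree: the same 11 h dose is corrected in AUC0-24 and AUC0-96 but not in AUC12-24 or AUC12-96. SAP 7.3.1 lists the computed AUCs by subject, so the disagreement would appear in the report.

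**Working it through.** **Inputs from the documents.** Protocol 10.5 gives 22 per arm, AUC12-96 of about 440 without drug effect, difference 110, SD 170 and one-sided alpha 0.05. SAP 7.3.1 gives the trapezoidal rule and the 4 hours. SAP 7.1.2 uses nominal assessment times, which SAP 7.2 sets at every 2 hours.

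**Assumed, because the documents give no figure.** Relief of 2-4 NPRS points after a dose, and the share of each arm rescued at 8-12 h.

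**The plan's own figure.** Noncentrality = 110 / (170 x sqrt(2/22)) = 110 / 51.26 = 2.146. A one-sided t-test with 42 degrees of freedom gives power of 68.0%, against the stated figure of about 67%. It reproduces. The documents give no figure for the carry-forward itself.

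**Scale.** The primary window is 84 h, so the planning mean is 440/84 = 5.24 points and the difference is 110/84 = 1.31 points. Pro rata (an assumption, since no AUC12-24 target is stated), AUC12-24 has mean 12 x 5.24 = 62.9 and difference 12 x 1.31 = 15.7.

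**Loss for one subject.** A dose before 12 h, carried for 4 hours, can reach only the 12 h and 14 h scores. In a trapezoid starting at 12 h with 2-hour steps, the 12 h score has weight 1 h and the 14 h score has weight 2 h.

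| Rescue time | Scores affected | Loss per point of relief | Loss for 2-4 points |
|---|---|---|---|
| 8 to <10 h | 12 h | 1 | 2-4 |
| 10 to <12 h | 12 h and 14 h | 1 + 2 = 3 | 6-12 |

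A dose at exactly 8 h counts only if the 4-hour limit includes its end point. The largest loss, 12 NPRS-hours, is 12/110 = 11% of the planned difference and 12/440 = 2.7% of the planning mean.

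**Worked case.** Rescue at 11 h, pre-rescue score 8, observed 4, 4, 5 at 12, 14, 16 h, then 5 to 24 h.

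- 7.3.1 read literally: 2 x (4+4)/2 + 2 x (4+5)/2 + 8 x 5 = 8 + 9 + 40 = 57.0.
- 7.1.1: 2 x (8+8)/2 + 2 x (8+5)/2 + 8 x 5 = 16 + 13 + 40 = 69.0.

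The gap of 12 equals 3 h x 4 points.

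**Shift in the arm difference.** If doses are spread evenly over 8-12 h, the mean weight is (1 + 3)/2 = 2 h. Shift = (placebo share - active share) x relief x 2 h.

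- 90% v 60%: 0.3 x 2 x 2 = 1.2 to 0.3 x 4 x 2 = 2.4.
- 90% v 40%: 0.5 x 2 x 2 = 2.0 to 0.5 x 4 x 2 = 4.0.
- Equal shares: 0.

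So 1.2-4.0 units, which is 1-4% of 110 and 8-25% of 15.7. Putting 110 - 1.2 and 110 - 4.0 into the power formula gives 67.1% and 65.2%, against 68.0%. As an extreme, if every placebo subject and no active subject is rescued at 10 to <12 h with 3 points of relief, the shift is 9 and power is 61.6%.

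**The case against.** The best reply is that there is no contradiction. SAP 7.3.1 does not say that carry-forward applies only to rescue inside the window, and it is silent on earlier rescue. SAP 7.1.1 fills that silence, covers AUC analyses and agrees with the Protocol. Read together, the three places carry the score across 12 h. This stands in part: it is a reasonable reading and probably the intended one. But 7.3.1 is the section a programmer will use for AUCs, and it states a condition that the other two lack. The precedence clause in SAP Section 3 ("the rules set forth in the specific section take precedence over the general policies") ranks specific sections over the Section 3 conventions. It does not rank 7.1.1 against 7.3.1, and by analogy it could be used to favour the narrower text.

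A second reply is that little depends on it. The SAP was written after early termination, with 23 subjects dosed and no testing, and the difference of 110 belongs to a 22-v-22 comparison that will not be run. In-patient scores, AUCs and rescue times are all listed by subject. This stands, and it limits the severity.

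A third reply is that full relief and the longest carry-over do not occur together: a dose just before 12 h leaves little relief in the 12 h score. This also stands, so 12 NPRS-hours is a ceiling.

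A reader might infer three stronger things, none of which the documents support. One is that relieved scores definitely enter the primary AUC; that needs 7.3.1 to be read as exclusive. Another is that 7.1.1 covers every kind of rescue. It covers protocol-specified rescue; under SAP Section 3, non-protocol rescue taken for inadequate relief means discontinuation from the efficacy portion. The third is that a full 4 hours of the window can be lost; the 2-hour grid limits the weight to 3 h.

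**Conclusion.** The point holds as a wording conflict that lets two competent programmers obtain different values of the primary endpoint from the same data. If 7.3.1 is applied literally, the loss is 1 NPRS-hour per point of relief for rescue at 8 to <10 h and 3 per point for rescue at 10 to <12 h, or 2-12 units for an assumed 2-4 points.

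The arm-level shift in AUC12-96 is about 1-4% of 110 under assumed shares of 90% v 40-60%. It is toward zero only if placebo subjects take more rescue in that span, and it vanishes if the shares are equal. The effect is relatively larger for AUC12-24, but the comparison there rests on a pro-rata difference that the plan does not state.

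No test or decision in this SAP depends on the result. Severity: minor.

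**What to change.** In SAP 7.3.1, replace the condition on when rescue is taken with: *used during, or within 4 hours before the start of, the AUC period*. Add that one carry-forward-adjusted NPRS profile and one NPRS-A profile are built per subject from time 0, and that every AUC window is cut from them. State whether a score at exactly 4 hours after the dose is included. This applies what 7.1.1 and the Protocol already imply and makes the nested AUCs agree.

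The cost is a few sentences in the SAP and a small programming change. It needs no new data and does not touch the rescue regimen. AUCs starting after time 0 may rise slightly in either group. If the database is already locked, state in the study report which rule was programmed.
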